9. MATERIALS AND METHODS

This study will use electronic means (online survey, email) and participants will receive a £20 Amazon voucher for completed participation. No face to face contact will occur between the research team and research participants. Participants will predominantly be recruited using JISC's online platform for connecting researchers with study participants (www.callforparticipants.com), as well as social media sites including Facebook and Instagram. Using these platforms, a research poster will be used to attract participants to the study and provide interested participants with a link to the screening questions, information sheet, consent form, and baseline survey. **See Appendix 7 to view the recruitment poster as it will be presented on www.callforparticipants.com, and shared on social media sites.**

The baseline survey (**see Appendix 1**) will collect the email addresses of interested participants. After submitting the baseline questionnaire, participants will be contacted via email with details about their group allocation and further instructions i.e. intervention participants will be instructed to complete 5-minute daily surveys each day for 14 days (see **Appendix 6, page 1** for instruction email template for intervention participants), whereas control group participants will be asked to continue as usual for 14 days (see **Appendix 6, page 2** for instruction email template for control participants). After the 14-day period both groups will be asked via email to complete the follow-up survey (**see Appendix 6, page 3**). The information sheet (**see Appendix 8**) and consent form (**see Appendix 9**) will precede the baseline survey and will provide full information about the nature of the study and details about what the participants in each group will be asked to do, including eligibility for the £20 incentive for taking part. The methodology for supplying participants with vouchers via email has been used in a previously approved study with no problems raised (ethics reference: 200401HR).

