10. PARTICIPANTS

Discuss the number of participants required, from where the participants will be recruited, and the exclusion and inclusion criteria. Please include power calculations where applicable.

Participants will be recruited using a research poster which will be presented both on JISC's research participant finder service: www.callforparticipants.com and social media sites: Facebook, Instagram and Twitter. **See Appendix 7 to view the recruitment poster as presented on www.callforparticipants.com, and shared on social media sites.** All participants who meet eligibility criteria and research terms will be provided with a £20 Amazon voucher after completing the study to thank them for their time.

Participants will be randomised using online resource: www.randomizer.org. Randomizer is a free resource for researchers in need of a quick way to generate random numbers or assign participants to experimental conditions. This site can be used for a variety of purposes, including psychology experiments, medical trials, and survey research. Randomizer works by generating a series of random unique numbers, therefore to allocate participants into the intervention group 1 set of 39 random numbers were generated using values ranging from 1-78. These figures were chosen following insights from the power analysis (see below).

Random number generation will be used to allocate participants into groups. Participants will be assigned a number when they join the study by submitting the baseline survey- this number will reflect the order in which they joined the study i.e. the first person to join will be assigned as number 1, the second will be assigned as number 2. This number will determine whether they are in the control or intervention group by using random numbers generated by randomizer.com. Randomizer works by generating a series of random unique numbers, therefore, to allocate participants into the intervention group, 1 set of 39 random numbers will be generated using values ranging from 1-78. If the participant's assigned number matches one of the 39 random numbers generated, they will be allocated into the intervention group. If their number is not on the random number list, they will be allocated into the control group.

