An a priori power analysis was conducted using G*Power 3 (Faul, Erdfelder, Lang, & Buchner, 2007) to test the difference between two independent group means (accounting for special, main effects, and interactions) using a two-tailed test, a medium effect size ($d = .40$) and an alpha of .05. Results suggested that a total sample of 52 participants with two equal sized groups of 26 was required to achieve a power of .80.

Medium effect sizes were estimated based on Cohen's (1962) conventional values because these values were derived from studies specific to psychological research (Aguinis, & Harden, 2009). Furthermore, medium effect estimates, rather than small estimates, were used for this research because this study is exploratory and small effects on symptom frequency might not be noticeable to participants. Small effects might imply that symptom monitoring as an intervention to help reduce menopausal symptoms may lack meaningful benefit.

Hoerger (2010) found evidence that at least 10% of participants will drop out of internet mediated research and such studies have high attrition rates. Furthermore, several studies have provided data on attrition rates of studies which employ a 2-week intervention period. Lancastle and Boivin's (2008) feasibility study aimed to establish whether a brief coping intervention (positive reappraisal coping intervention; PRCI) was acceptable and practical when evaluated in the context of a randomised trial. Of the 84 women who agreed to participate in the study 55 (65.5%) completed all measures, suggesting an attrition rate of 34.5%. Moreover, Lancastle's (2006) study also evaluated the PRCI alongside a positive mood inductive intervention, and a daily monitoring control group; this research reported a 31% attrition rate.

Therefore, taking into account average attrition rates from internet mediated research (10%), as well as studies which have utilised a 2-week intervention period (33%), it was decided that the proposed study will use a total sample of 78 participants with two equal groups of 39.

11. HAVE NATIONALLY APPROVED / REGULATORY BODY GUIDELINES BEEN FOLLOWED IN PREPARING THIS PROTOCOL?

(E.g. Association of the British Pharmaceutical Industry Guidelines (1983), Royal College of Physicians Guidelines, The Declaration of Helsinki, British Psychological Society guidelines, BERA, etc.). If so, please specify.

- Faculty of Life Sciences and Education Ethics Committee

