Appendix 14: The risk assessment table. [Page 98](#)

Appendix 1: The baseline survey in Word document format:

FACULTY OF LIFE SCIENCES AND EDUCATION
FACULTY ETHICS SUB GROUP APPLICATION FORM

Baseline questionnaire

Demographics:

4. Please type your email address (this is required to continue with this study)

.....

5. How would you describe your physical and mental health in general?

- Good
- Okay
- Poor

6. What is your living status?

- I live alone
- I live with my family
- I live with friends
- I live with my partner
- I live in shared housing
- I live in a residential home

7. What is your relationship status?

- In a relationship
- In a relationship and living together
- Married
- Divorced or separated
- Widowed
- Single

8. What is your current occupation? Tick as many as apply:

- Working full-time
- Working part-time
- Student
- Military
- Volunteer
- Looking for work
- Homemaker
- Retired

**FACULTY OF LIFE SCIENCES AND EDUCATION
FACULTY ETHICS SUB GROUP APPLICATION FORM**

- Unable to work due to illness or disability
- Full-time carer for a family member/ loved one
- Other

8b. If you selected Other, please specify:

.....

9. What is your ethnicity?

- White
- Asian
- Black
- Mixed ethnicity
- Other

9a. If you selected Other, please specify:

.....

10. What was the date of your last menstrual period? If you can't remember exactly please give your best estimate:

.....

11. Please type the name of the country and the town/city you live in:

.....

12. Are you currently using any medication or treatments for your menopause symptoms?

- No
- Yes

12a. If you selected Yes, please specify which medication or treatments you are using. Examples can include HRT, antidepressants, psychological treatments, counselling, or supplements.

.....

13. Please describe any health conditions that you are currently being treated for:

.....

**FACULTY OF LIFE SCIENCES AND EDUCATION
FACULTY ETHICS SUB GROUP APPLICATION FORM**

14. Please describe any non-menopause-related medications or treatments you are currently using:

.....

You are now going to be asked some questions about your health and you as a person, please work through them, giving the answer that best applies to you for each question.

Mood questionnaire:

15. Describe yourself as you generally are now, not as you wish to be in the future. Describe yourself as you honestly see yourself, in relation to other women of your age. Indicate for each statement whether it is:

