Appendix 6: Participant information email templates

Appendix 6: Participant information email templates
Email template advising intervention group participants of their group allocation, and instructing them to complete the DRK survey each day for 14 days:

Hi,
Thank you for participating in our study.
You have been allocated into the intervention group.
Your username is: **pilot1**
Please remember this username as it will be used to provide you with your £20 Amazon voucher, you can contact [contact] if you forget it.
Starting from today, you will be asked to complete a 5-minute survey each day for the next 14 days. You must complete and return each survey within 24 hours of receiving the link via email. There will be a different link each day. You may open the **Day 1** survey in your web browser now by clicking the link below:

<https://southwales.onlinesurveys.ac.uk/daily-record-keeping-form-preview>

If the link above does not work, try copying this link into your web browser:

<https://southwales.onlinesurveys.ac.uk/daily-record-keeping-form-preview>

This link is unique to you and should not be forwarded to others

Please do not reply to this email. If you would like to withdraw your data, please email [contact]. You can also email [contact] if you would like to opt out of receiving text message reminders.

If you have any questions or concerns about this study, please email: [REDACTED]

We thank you again for your participation,

**FACULTY OF LIFE SCIENCES AND EDUCATION
FACULTY ETHICS SUB GROUP APPLICATION FORM**

The Research Team

The email template advising control participants of their group allocation, and instructing them to carry on as usual for 14 days:

Thank you for participating in our study.

You have been allocated into the **control** group.

Your username is: **pilot1**

Please remember this username as it will be used to provide you with your £20 Amazon voucher, you can contact [contact] if you forget it.

For the next 14 days, please continue with your life as usual. Once the 14-day period has passed you will receive a link to a follow-up survey via email.

Once you have completed the follow-up survey you will be provided with your **£20 Amazon gift voucher via email**, provided you have completed it within the allocated time frame and have met the terms and conditions (see the information sheet attached for further guidance).

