
requests that she is unable to grant.
 
For example, participants will be answering health and medical type questions (i.e. "have your menopause symptom become better or worse?"). This may lead some to mistake the intent of the survey, and email the lead researcher to ask for medical advice.
 
Participants might also email [name] wishing to complain to her if they do not meet the conditions for remuneration, or they
	
by survey participants, for example, survey respondents may request medical advice. Therefore, provisions will be made in the event that this occurs. [name] also could be approached by participants wishing to complain and pressurise her into providing remuneration for which they are not eligible, and control participants might feel disappointed that they were not given an opportunity to engage in the daily monitoring intervention, and they may approach [name] wishing to complain or pressurise her into
	
will be directed to the Director of Studies ([name]) in the first instance. Participants will be asked only to contact [name] with questions about procedural points. If participants have any questions about anything related to the survey (i.e. symptom monitoring or the menopause) they will be asked to contact the Director of Studies: [name]. If any participants have questions which are not related to the survey or if they have objections, then the lead researcher will consult with her supervisors and a joint decision will be made about the best way to solve the problem, with escalation to the USW research governance officer if this isn't solved satisfactorily. It will be clearly stated in the information sheet that the research team cannot provide medical advice and that any respondents who are concerned should contact their GP.
 
In terms of complaints about eligibility for/claiming the voucher, the steps participants need to take to ensure they are eligible to claim the voucher are clearly stated on the information sheet and repeated in the debrief sheets, minimising the likelihood that participants could claim they didn't know they had to satisfy certain criteria to be eligible for remuneration. Together, these controls should
			
The information sheet and debrief forms, as well as all emails sent to participants, will include the terms and conditions for voucher eligibility:
 
You will be emailed your £20 Amazon gift voucher within the next 24 hours. Make sure you check your junk/spam folder if you have not received it after 24 hours, if you have still not received it please email [contact]. Only one £20 voucher will be provided per participant. Amazon vouchers will be sent to those who fully completed the research materials sent to them via email, did not withdraw from the study, and had accurately confirmed their username on each survey they submitted.
 
"To be eligible for the voucher you must satisfy the following criteria: You must not withdraw or drop-out from this study. You must complete and submit all surveys which are sent to you within the stated time periods. You will have had 24 hours to complete the follow-up survey. If you were allocated into the intervention group you must have completed the 5-minute surveys each day (within 24 hours of the survey being received via email) for 14 days. You must have accurately confirmed your username on each survey you completed. Your username will remain
	

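### Allocation numbers are used at baseline submission, before the typed email address is shown to work; one confirmation email first would move unreachable women from post- to pre-randomisation loss

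*Combined protocol and SAP*

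**What the plan says.** Section 10 (Participants) ties randomisation to the survey: "Participants will be assigned a number when they join the study by submitting the baseline survey". The list is fixed: "1 set of 39 random numbers will be generated using values ranging from 1-78". Everyone else is a control: "If their number is not on the random number list, they will be allocated into the control group".

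Appendix 1, item 4, collects the address in one free-text field: "Please type your email address (this is required to continue with this study". Section 9 gives the next step: "After submitting the baseline questionnaire, participants will be contacted via email with details about their group allocation and further instructions". It has the allocation email sent within 24 hours of the baseline survey. It is the first email shown in the documents.

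That email differs by arm (Appendix 6). For monitoring women it holds the Day 1 survey link, starts the 14 days at once, and adds: "You must complete and return each survey within 24 hours of receiving the link via email". For controls it asks only that they carry on as usual. Their next email comes after 14 days and repeats the username and link (Appendices 6 and 13).

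Section 27 defines adherence in the monitoring arm as all 14 daily surveys, each within 24 hours. Section 10 excludes from analyses anyone who leaves study materials incomplete or does not comply fully. Section 8 adds a 5pm text with the survey link for monitoring women, and Appendix 1, item 26, makes this optional. Section 19 starts the 15-day period at baseline submission.

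**The concern.** A woman who mistypes her address, or whose study mail is always filtered, tells us nothing about monitoring. If she is lost before randomisation, the cost is recruitment time and the comparison is untouched. If she is lost afterwards, she is a missing outcome in a fixed total of 78.

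The late-read first email is the more awkward case. The same event removes a monitoring woman from the analysis and leaves a control unaffected. Exclusion then depends on arm from the first day, and the women removed may differ from those kept in engagement or symptoms. The 33% attrition allowance is applied equally to both arms, so it covers numbers lost but not a difference between arms.

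**Working it through.** **Inputs from the documents.** 52 analysable women needed, 33% attrition and 78 randomised as 39 per arm (Section 10, power analysis); exclusion for incomplete compliance (Section 10); 14 of 14 surveys on time (Section 27); the 24-hour limit from the first email (Appendix 6).

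**Inputs assumed, because the documents give none.** The share of entrants who are non-starters, *u*: 5% or 10%. The share of monitoring women who do not act on the first email in time, *v*: 5% to 20%.

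**The plan's own figure.** 52 / (1 − 0.33) = 77.6, rounded up to 78, so the inflation reproduces. Conversely, 78 × 0.67 = 52.3. (Whether 52 follows from the printed effect size is a separate matter.)

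**A. Non-starters, if they fall within the 33%.** Analysable women = 78 × 0.67 / (1 − *u*); loss after randomisation = 1 − 0.67 / (1 − *u*); standard-error ratio = √(1 − *u*).

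| *u* | Analysable of 78 | Loss after randomisation | Standard-error ratio |
|---|---|---|---|
| 0 (as planned) | 52.3 | 33% | 1 |
| 5% | 52.26 / 0.95 = 55.0 | 29.5% | 0.975 |
| 10% | 52.26 / 0.90 = 58.1 | 25.6% | 0.949 |

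**B. First email not acted on in time, monitoring arm only.** Expected exclusions = 39 × *v*. With 33% other loss in both arms, the control arm keeps 39 × 0.67 = 26.1 and the monitoring arm keeps 26.1 × (1 − *v*).

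| *v* | Monitoring women excluded | Analysed, monitoring v control |
|---|---|---|
| 5% | 2.0 | 24.8 v 26.1 |
| 10% | 3.9 | 23.5 v 26.1 |
| 15% | 5.9 | 22.2 v 26.1 |
| 20% | 7.8 | 20.9 v 26.1 |

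No control is excluded for this reason in any row.

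**C. Non-starters on top of the 33%.** With 5% dead addresses in both arms and 10% unread first emails in monitoring, controls are 39 × 0.95 × 0.67 = 24.8, and monitoring women are 24.8 × 0.90 = 22.3.

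**D. Recruitment needed with a confirmation step.** 78 / 0.95 = 82.1, so 83 submissions; 78 / 0.90 = 86.7, so 87.

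**E. Age of the baseline symptom record at Day 1.** 72 hours to confirm (the proposed window) plus the existing 24 hours to send the allocation = 96 hours, or about 4 days.

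**The case against.** Randomising after consent and a full baseline survey contradicts nothing in the plan, and several stronger readings fail.

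- **That the team expects study mail to be filtered.** A reader might infer this from Appendix 14: "Make sure you check your junk/spam folder if you have not received it after 24 hours". That line concerns the voucher email at the end of the study, not the allocation or daily emails, so it is no evidence on how often the first email is missed.
- **That all non-delivery falls on the monitoring arm.** It does not. A control with a dead address never gets her follow-up link, so that loss is two-sided. Only a first email read late is one-sided.
- **That the plan gives a 10% non-starter rate.** Section 10 says "at least 10% of participants will drop out of internet mediated research". That is drop-out, stated as a minimum. Nothing shows how much of it, or of the 33%, is failure to start.
- **That an unread email means a lost Day 1.** The 5pm text prompts women who gave a mobile number. This mitigation is real but partial: the text template in Appendix 5 carries no username, and Appendix 4 says a form without it is not valid.

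Two further objections stand. The information sheet, consent form and debrief sheets are not in the text reviewed, and Appendix 1 is a Word copy of the live survey, so an address check elsewhere cannot be ruled out. And the exclusion arises from the full-compliance rule, which a confirmation step leaves in place: Day 1 and later emails can still be missed.

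**Conclusion.** The point holds as a cheap improvement, not as an error in the plan. On the text available, a number is used before the address is shown to work, and the plan's own rules make a late-read first email costly in one arm only. That step reads the adherence definition in Section 27, written for the voucher, together with the exclusion rule in Section 10.

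The size is not known. On the assumed rates, filtering non-starters first would gain about 3 to 6 analysable women and shrink standard errors by about 2.5% to 5%. An unread first email would exclude about 2 to 8 of 39 monitoring women, before any are rescued by a text.

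A reader might infer that the trial must fall short of 52, or that its result is biased. The documents support neither: the 33% allowance may already contain the non-starters, and the direction of any bias from the excluded women cannot be determined.

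**What to change.** Amend Sections 9, 10 and 19 together:

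- On receipt of an eligible baseline survey, send one email with a confirmation link or code.
- Assign the next number, and send the allocation, only after she confirms within a short stated window, for example 72 hours.
- Start the 15-day period at allocation in both arms, instead of at baseline submission.
- Report unconfirmed entries as not randomised; they take no number.
- Continue until 78 confirmed women have been allocated.

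The total randomised is unchanged. The cost is one more template email and about 83 to 87 submissions at 5% to 10% non-confirmation. Those extra entries must fit a recruitment window that Section 20 closes when analysis starts in December 2020. The baseline symptom record may be up to about 4 days old at Day 1, equally in both arms.

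The step reduces arm-dependent loss but does not remove it, because the full-compliance exclusion still applies to surveys missed later. Section 15 says the recruitment platform supplies contact details, while Sections 9 and 17 say the baseline survey collects them; this should be reconciled in the same amendment.

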- **Perceived effects of research engagement:** Three items (to be completed after the 2-week research period) will assess whether research participation has led to any perceived improvements in emotional and physical well-being: "Since your engagement in this research, what changes have you noticed in your physical or emotional well-being? "If you have experienced any changes, why do you think these changes occurred?" and "what impact has participating in this research had on your physical or emotional well-being?". These items will allow for more specific assumptions to be made about whether the use of symptom monitoring in research is attributed to perceived improvements, and whether researchers employing symptom monitoring as a control intervention should be wary of this occurrence. **To view how the research engagement questions will be presented on the follow-up**

FACULTY OF LIFE SCIENCES AND EDUCATION
FACULTY ETHICS SUB GROUP APPLICATION FORM

survey, see Appendix 3, page 8.

- **Covid-19 experience question:** A final qualitative item will also be used to assess participants' experiences in dealing with the menopause during the Covid-19 pandemic: "Experiencing the menopause during the Covid-19 pandemic might be especially challenging for some women. Please use this space to tell us more about this experience if you wish. E.g., did you feel able to consult a GP when you needed to? Did any changes due to work restrictions or changes in home circumstances feel different because of the menopause? Did the menopause make you feel more or less able to cope?". This item was included in order to gain perspective on the wider context in which this research is taking place, in order to understand how the 2020 pandemic has impacted research findings. **To view the Covid-19 experience question as it will be presented on the follow-up survey, see Appendix 3, page 8.**

